5.2.2.1 Dose Delay or Interruption

Please refer to section 6.3 of the protocol.

5.2.3 Dexamethasone

Dexamethasone will be obtained from commercial supply in this study. This may lead to added costs for the participant or the participant's insurance company.

Dexamethasone will be given as a single oral dose of 40mg on days 1, 8, and 15 of each 28 day cycle during the induction phase of this study (Cycles 1-6 only).

Dexamethasone should be taken at approximately the same time each day. It is recommended that dexamethasone be taken in the morning to reduce insomnia. Each dose should be taken with food. If a dose of dexamethasone is vomited, the participant should continue with the regular schedule of the drug at the next dose. If a dose is missed and less than 12 hours has elapsed since the missed dose, the patient may take the dose for that day. If more than 12 hours has elapsed since missing a dose at the normal time, the patient should not take the dose, but take the next dose at the normal time on the following day. If a dose is missed, it should be taken as soon as possible on the same day. If a dose is vomited, the dose should not be made up and the participant should continue with the regular schedule of the drug at the next dose.. A drug diary must be provided to participants to record oral administration of doses. Dose modification guidelines are described in Section 6.3.

CONFIDENTIAL

This document is confidential. Do not disclose or use except as authorized.

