5.2.2 Lenalidomide

Lenalidomide will be obtained from commercial supply in this study. This may lead to added costs for the participant or the participant's insurance company.

Lenalidomide will be given as a single daily oral dose of 25 mg per day on days 1-21 followed

CONFIDENTIAL

This document is confidential. Do not disclose or use except as authorized.

by a 7-day rest period for induction (cycles 1-6) and 15 mg per day on days 1-21 for maintenance (cycles 7-12) (if a patient was dose reduced during the induction phase for lenalidomide below 15mg, then maintenance phase starts at that dose reduction and not at the higher 15 mg dose). Please refer to Table 17 for specific hold and delay instructions for lenalidomide. Dose modification guidelines are described in Section 6.3.

Lenalidomide capsules should be swallowed whole, and should not be broken, chewed or opened. Administration of lenalidomide should be at approximately the same time each day. Drug may be taken with or without food. If a dose is missed and less than 12 hours has elapsed since the missed dose, the patient may take the dose for that day. If more than 12 hours has elapsed since missing a dose at the normal time, the patient should not take the dose, but take the next dose at the normal time on the following day. If a dose is missed, it should be taken as soon as possible on the same day. If a dose is vomited, the dose should not be made up and the participant should continue with the regular schedule of the drug at the next dose. A drug diary must be provided to participants to record oral administration of doses.

Participants who take more than the prescribed dose of lenalidomide should be instructed to seek emergency medical care if needed and contact study staff immediately. Participants experiencing adverse events may need study treatment modifications (see Section 6.3).

Lenalidomide related resources must be provided to all patients prior to receiving lenalidomide therapy as part of the Revlimid REMS program. For more information regarding program registration and drug ordering, refer to section 8.2.

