8.3.7 Administration

During induction therapy, participants will receive dexamethasone as a single oral daily dose of 40mg on Days 1, 8 and 15 of cycles 1-6.

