Study Drug Administration	
Agent Administration Guidelines are found in Section 5.2
 
 • Nivolumab is given IV every other week on Days 1&15; Lenalidomide is PO Days 1-21; Dexamethasone is PO Days 1, 8, 15 for Cycles 1-6 ONLY • Nivolumab is given IV over 60 minutes (+/- 10 minutes); No standard premeds required, unless history of infusion reaction. A 60 min post-infusion observation period is suggested, especially during first 2 cycles, but not mandatory per protocol. • The drugs may be administered in any order. • Criteria to treat DAY 1: ANC\geq1,000; PLT\geq50; Other drug related, non-heme tox \leqGrade 1 or baseline. • Criteria to treat DAY 15: For Lenalidomide: ANC\geq1,000; PLT\geq30; Hgb\geq8 Other drug related less than Grade 3 or baseline. For Nivolumab: AST\leq90; ALT\leq156; Bilirubin\leq1.8; Creatinine\leq1.95 or \leq1.5 x baseline • Fasting is not required. • Lenalidomide capsules and Dexamethasone tablets should be swallowed whole, and should not be broken, chewed or opened. Administration should be at approximately the same time each day. If a dose is missed and less than 12 hours has elapsed since the missed dose, the patient may take the dose for that day. If more than 12 hours has elapsed since missing a dose at the normal time, the patient should not take the dose, but take the next dose at the normal time on the following day. If a dose is missed, it should be taken as soon as possible on the same day. If a dose is vomited, the dose should not be made up and the participant should continue with the regular schedule of the drug at the next dose.
Dose Mods & Toxicity	
Dose Modifications/Dosing Delay for Toxicity are outlined in Section
 
 • This protocol uses NCI CTCAE criteria, version 4.03 • There are no dose modifications for Nivolumab, there are dose reductions per protocol for Lenalidomide and Dexamethasone.
Con Meds	
Concomitant Therapy Guidelines are in Section 5.3.1
 
 • Stem cell mobilization and collection may be performed at time of best response or after 6 cycles of therapy. • Filgrastim is allowed, pegfilgrastim is NOT. • Transfusions and supportive care are allowed; bisphosphonate therapy included.

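### The missed-dose instructions for lenalidomide and dexamethasone contradict each other for morning doses, and the dexamethasone rule sends the patient to a day that is never a dosing day (wrong as written, low severity)

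*Combined protocol and SAP*

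**What the plan says.** Section 5.2.3 gives dexamethasone as a "single oral dose of 40mg on days 1, 8, and 15 of each 28 day cycle" during induction. It adds: "It is recommended that dexamethasone be taken in the morning to reduce insomnia". Section 8.3.7 repeats the schedule ("single oral daily dose of 40mg on Days 1, 8 and 15 of cycles 1-6"), and so does the special nursing considerations page ("Dexamethasone is PO Days 1, 8, 15 for Cycles 1-6 ONLY").

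The missed-dose text in 5.2.3 has three parts:

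- If "less than 12 hours has elapsed since the missed dose, the patient may take the dose for that day".
- Beyond 12 hours, "the patient should not take the dose, but take the next dose at the normal time on the following day".
- Immediately afterwards: "If a dose is missed, it should be taken as soon as possible on the same day".

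The same three parts appear for lenalidomide in 5.2.2. They appear again on the nursing page under Study Drug Administration, in one paragraph that covers both drugs. Lenalidomide is taken once daily on days 1 to 21 of a 28-day cycle. In 5.2.2 and 5.2.3, and on the nursing page, a vomited dose is not made up.

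**The concern.** These are working instructions for drugs that patients take at home, at several sites. An instruction of this kind should lead to one action. Here the last sentence has no time limit and cancels the 12-hour cutoff for part of the day. The words naming the following day suit a daily drug and do not suit one given on days 1, 8 and 15. Two sites could each follow the text and advise a patient differently, and a monitor would have no single standard against which to call a deviation. For dexamethasone, a patient who does exactly what is written takes a dose on an unscheduled day. The stake is dosing clarity and a modest gain in dosing safety; the statistical conclusions are not at risk.

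**Working it through.** The plan states no figure on this point, so there is none to reproduce. The check compares the sentences with each other and with the dosing calendar.

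**1. The two rules against the clock.** Let T be the normal dose time in hours after midnight and d the delay in hours.

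- Rule A (12-hour rule): the dose is allowed if d < 12 and forbidden if d > 12.
- Rule B (same-day sentence): the dose is directed as long as T + d < 24.
- They conflict when d > 12 and T + d < 24, that is, from clock time T + 12 until midnight. The length is 24 − (T + 12) = 12 − T hours, which is positive only for T < 12.

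The protocol gives no dosing hour, so the following times are assumptions: 06:00 gives 12 − 6 = 6 hours, 08:00 gives 4 hours, 10:00 gives 2 hours, and noon gives 0. With a delay under 12 hours on the same day, Rule A permits the dose and Rule B directs it, and a patient can satisfy both by taking it.

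**2. The following day against the dexamethasone schedule.** This step needs no clock assumption.

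| Missed dose | Following day | Scheduled? | Next scheduled day |
|---|---|---|---|
| Day 1 | 1 + 1 = 2 | No | Day 8 |
| Day 8 | 8 + 1 = 9 | No | Day 15 |
| Day 15 | 15 + 1 = 16 | No | Day 1 of the next cycle |

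The wording fails for 3 of 3 dexamethasone doses. For lenalidomide the following day is a dosing day after 20 of the 21 doses. This suggests that daily-drug wording was carried into the dexamethasone section. Two other features of 5.2.3 point the same way. It speaks of taking dexamethasone at about the same time each day, and it refers the reader to 6.3 (lenalidomide) for dose modification although the dexamethasone rules are in 6.4.

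The off-schedule dose would be 40 mg at the starting level, or 20 or 10 mg at the reduced levels in Table 16.

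**3. Whether another section settles it.**

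- Section 6.3 covers lenalidomide that is held for toxicity; such doses count as missed and are not made up.
- Section 6.4 covers dexamethasone changes for toxicity.
- Section 6.5 and Table 17 cover nivolumab delays.
- Sections 8.2.7 and 8.3.7 restate the schedules.

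None of them says which missed-dose rule prevails or corrects the following-day wording.

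**4. Who is still affected.** The version is dated 23 January 2018, and accrual stopped in September 2017 (1.1 and 5.1). Assume the last patient started on 30 September 2017 with no delays.

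- The last scheduled dexamethasone dose, cycle 6 day 15, is treatment day 5 × 28 + 15 = 155, or 3 March 2018. That is 39 days after the version date.
- Appendix E, 3.2 allows 90 days from notification for a revision that is not life-threatening. If notice went out on the version date, that limit is 23 April 2018.
- Cycle 12 ends on treatment day 12 × 28 = 336, about the end of August 2018.

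On these assumptions, scheduled induction dexamethasone could be over before the change takes effect everywhere, while scheduled lenalidomide continues beyond it. Section 5.1 also lets participants elect to remain on lenalidomide and dexamethasone, and allows dexamethasone to be re-added in maintenance on days 1, 8 and 15.

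**The case against.** The strongest reply is that a sensible reader copes. The same-day sentence can be read as subordinate to the 12-hour rule, and the dexamethasone days are fixed in 5.2.3, in 8.3.7 and in the same table cell of the nursing page as the rule itself. Site staff go over the printed package instructions when lenalidomide is dispensed (8.2.7). The patient diary is not in the documents, so it is unknown whether patients saw both sentences, and no missed-dose frequency is given. The correction may also come too late for most scheduled dexamethasone. All of this stands as a limit on importance. It does not make the text consistent: nothing says that one sentence yields to the other, and the following-day wording cannot be squared with days 1, 8 and 15.

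A reader might infer more in three places, and the documents do not support it:

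- *That evening doses produce the opposite contradiction after midnight.* They do not. The 12-hour rule gives permission, and the same-day sentence asks for promptness without forbidding anything after midnight.
- *That the text lets a missed dexamethasone dose be made up a day late.* It says the missed dose should not be taken. What is wrong is the date given for the next dose.
- *That a missed day-21 lenalidomide dose leads to dosing on day 22.* This is strained. Sections 5.2.2 and 8.2.7 confine dosing to days 1 to 21, so there is no next dose on day 22 to take.

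**Conclusion.** The point holds as a low-severity error in wording, in 5.2.2, 5.2.3 and the nursing page. For dose times before noon, the two sentences conflict from 12 hours after dose time until midnight. The number of hours depends on a dose time that the protocol does not state. The dexamethasone error, in 5.2.3 and in the shared nursing text, rests on no assumption: the named day is off schedule for every dose.

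It would be wrong to infer that the trial's results are compromised. The 2-year progression-free endpoint, the 39-patient rule and its error rates do not depend on this text, and nothing in the documents shows that any patient was misdosed. At this version the correction reaches only patients still taking lenalidomide, or continuing or re-added dexamethasone, and the documents do not say how many that is.

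**What to change.** In 5.2.2, 5.2.3 and the special nursing considerations page:

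- Delete the sentence "If a dose is missed, it should be taken as soon as possible on the same day".
- Keep the 12-hour rule.
- Where the rule names the following day, write *on the next scheduled dosing day*. For dexamethasone, add that this means day 8, day 15, or day 1 of the next cycle.

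A dose not taken within 12 hours is then skipped, in line with the existing treatment of vomited doses and of held lenalidomide.

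The cost is a wording amendment in three places, and in the diary if it repeats the text. It needs routine IRB approval and implementation at participating institutions within the 90 days set in Appendix E, 3.2. Study procedures and visits stay as they are. Since remaining dexamethasone exposure may be short, it makes sense to notify sites promptly or to carry the change in the next amendment already planned.

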5.2.3.1 Dose Delay or Interruption

Please refer to section 6.4 of the protocol.

5.3 General Concomitant Medication and Supportive Care Guidelines

5.3.1 Medications and supportive care

- Patients who experience worsening neuropathy from baseline should be observed for recovery, have dose reductions/delays as indicated in the protocol, and any supportive therapy or intervention may be initiated as appropriate at the discretion of the investigator.
- Supportive measures consistent with optimal patient care may be given throughout the study.
- Stem cell collection may be performed at the time of best response (PR, VGPR or CR or at the investigator's discretion) or after 6 cycles of therapy for those who are transplant eligible, and/or who plan to pursue transplant in the future. The standard mobilization procedures of the treating institution should be followed. Plerixafor should be the preferred mobilization agent, though cyclophosphamide or other agent may be used at the investigator's discretion. A delay of no more than 3 weeks is allowed between the end of collection and re-initiation of therapy especially if chemotherapy such as high dose cyclophosphamide was used for stem cell mobilization. Mobilization should occur as soon as possible after study treatment is stopped.
- Use of white cell growth factors (Filgrastim or acceptable equivalent) is allowed for management of treatment-induced neutropenia at physician discretion. Filgrastim or equivalent should be given according to local institutional guidelines or per the package insert. Pegfilgrastim is not to be used in place of filgrastim.
- Patients may be transfused with red cells and platelets as clinically indicated and according to institutional guidelines.
- Patients may receive bisphosphonates per recommendations of myeloma therapy, or may follow local standard of care. A note should be placed about patients who are not receiving bisphosphonates, such as osteonecrosis of the jaw.
- If nausea and/or vomiting is/are noted at any point in time, premedication with prochlorperazine or other antiemetics may be used before future doses. Antiemetics, including 5-HT3 serotonin receptor antagonists, may be used as needed at the discretion of the investigator.

CONFIDENTIAL

This document is confidential. Do not disclose or use except as authorized.

- If nausea persists in spite of the use of standard antiemetics, additional symptom management should be initiated per institutional standard.
- Loperamide or other antidiarrheal may be used for symptomatic diarrhea at discretion of the investigator. The dose and regimen will be according to institutional guidelines. IVF may be given to prevent volume depletion.
- Thromboprophylaxis is recommended for all participants. Thromboprophylactic initiation and regimen choice is at the discretion of the treating physician or sites may follow the current package insert for Revlimid. It is recommended that if the platelet count falls below 30,000/mm³, thromboprophylaxis be held to minimize the risk of bleeding and then resumed when platelet counts are equal to or above 30,000/mm³.
- Nonsteroidal anti-inflammatory drugs (NSAIDs) should be avoided with impaired renal function given reported NSAID-induced renal failure in patients with decreased renal function.
- Patients may be at an increased risk of infection including reactivation of herpes zoster and herpes simplex viruses. Antiviral therapy such as acyclovir, valacyclovir, or other antivirals may be initiated as clinically indicated at the discretion of the treating investigator. Antivirals for other indications are also allowed.

• **The following procedures are prohibited during the study:**

- Any antineoplastic treatment with activity against MM, other than study drugs
- Radiation therapy (note that, in general, the requirement for local radiation therapy indicates disease progression)

5.4 Management of Clinical Events

5.4.1 Rash

- Symptomatic measures such as antihistamines or corticosteroids (oral or topical) have been successfully used to manage rash and have been used prophylactically in subsequent cycles. The use of a topical, IV, or oral steroid (eg, prednisone \leq 10 mg per day or equivalent) is permitted.
- Management of a Grade 3 rash may require intravenous antihistamines or corticosteroids. Administration of lenalidomide (and/or other causative agent

CONFIDENTIAL

This document is confidential. Do not disclose or use except as authorized.

if given in combination) should be modified per protocol and re-initiated at a reduced level from where rash was noted.

- In line with clinical practice, a dermatology consult that includes a biopsy of Grade 3 or higher rash or any SAE involving rash is recommended. Prophylactic measures should also be considered if a patient has previously developed a rash (eg, using a thick, alcohol-free emollient cream on dry areas of the body or oral or topical antihistamines).
- A rare risk is Stevens-Johnson Syndrome, a severe and potentially life-threatening rash with skin peeling and mouth sores, should be managed symptomatically according to standard medical practice. Punch biopsies for histopathological analysis are encouraged at the discretion of the investigator.

5.4.2 Thrombocytopenia

- Blood counts will be monitored regularly as outlined in the protocol with additional testing obtained according to standard clinical practice. Thrombocytopenia may be severe but has been manageable with platelet transfusions according to standard clinical practice. Lenalidomide administration should be modified as noted as per dose modification recommendations in the protocol when thrombocytopenia occurs (see Section 6.3). Therapy may be reinitiated at a reduced level upon recovery of platelet counts.
- A rare risk is thrombotic thrombocytopenic purpura (TTP), a rare blood disorder where blood clots form in small blood vessels throughout the body characterized by thrombocytopenia, petechiae, fever, or possibly more serious signs and symptoms. TTP should be managed symptomatically according to standard medical practice.

5.4.3 Neutropenia

- Blood counts will be monitored regularly as outlined in the protocol with additional testing obtained according to standard clinical practice. Neutropenia may be severe but has been manageable. Growth factor support is not required but may be considered according to standard clinical practice. Lenalidomide administration should be modified as per dose modification recommendations in the protocol when neutropenia occurs (see Section 6.3).

5.4.4 Pregnancy

- Female patients participating in this study should avoid becoming pregnant, and male patients should avoid impregnating a female partner. Non-sterilized female patients of reproductive age group and male patients should use effective methods of contraception through defined periods during and after study treatment as specified below.

CONFIDENTIAL

This document is confidential. Do not disclose or use except as authorized.

- Female patients must meet 1 of the following:
 - Postmenopausal for at least 1 year before the screening visit
 - Surgically sterile
 - If they are of childbearing potential, agree to practice 2 effective methods of contraception from the time of signing of the informed consent form through 120 days after the last dose of lenalidomide (Revlimid) of study drug
 - Women who are of childbearing potential, agree to practice contraception for a period of 5 months after their last dose of nivolumab
 - Agree to practice true abstinence, when this is in line with the preferred and usual lifestyle of the subject.
 - Periodic abstinence (eg, calendar, ovulation, symptothermal, postovulation methods) and withdrawal are not acceptable methods of contraception.
- Male patients, even if surgically sterilized (ie, status postvasectomy) must agree to 1 of the following:
 - Practice effective barrier contraception during the entire study treatment period and through 154 days after the last dose of lenalidomide (Revlimid)
 - Men receiving nivolumab who are sexually active with women of childbearing potential must adhere to contraception for a period of 7 months after the last dose of nivolumab
 - Agree to practice true abstinence, when this is in line with the preferred and usual lifestyle of the subject.
 - Periodic abstinence (eg, calendar, ovulation, symptothermal, postovulation methods for the female partner) and withdrawal are not acceptable methods of contraception.

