3.1.3 ECOG Performance Status (PS) 0, 1, or 2 (Appendix A)

3.1.4 The following laboratory values obtained ≤ 21 days prior to registration and confirmed prior to the first dose of study drug:

- ANC $\geq 1000/\mu\text{L}$
- PLT $\geq 50,000/\mu\text{L}$. Platelet transfusions to help patients meet eligibility criteria are not allowed within 3 days before study enrollment.
- Total bilirubin ≤ 1.5 mg/dL (If total is elevated check direct and if normal patient is eligible.)
- AST $\leq 3 \times$ institutional upper limit of normal (ULN)
- ALT $\leq 3 \times$ institutional upper limit of normal (ULN)
- WBC $\geq 2000/\mu\text{L}$

3.1.5 Ability to understand and willingness to sign a written informed consent before performance of any study-related procedure not part of normal medical care, with the understanding that consent may be withdrawn by the subject at any time without prejudice to future medical care.

CONFIDENTIAL

This document is confidential. Do not disclose or use except as authorized.

3.1.6 Female patients who are postmenopausal for at least 1 year before the screening visit or are surgically sterile. Females of childbearing potential* must have a negative serum or urine pregnancy test with a sensitivity of at least 25 mIU/mL within 10 – 14 days and again within 24 hours prior to prescribing lenalidomide for Cycle 1 (prescriptions must be filled within 7 days as required by Revlimid REMS®) and must either commit to continued abstinence from heterosexual intercourse or begin TWO acceptable methods of birth control, one highly effective method and one additional effective method AT THE SAME TIME, at least 28 days before she starts taking lenalidomide. Females of reproductive potential must agree to follow instructions for method(s) of contraception for the duration of treatment with any study drug(s) plus 5 half-lives of study plus 30 days (duration of ovulatory cycle) for a total of 120 days after their last dose of lenalidomide (Revlimid). Women must not breastfeed.

Female patients who are of childbearing potential must use contraception for 5 half-lives plus 30 days after their last dose of nivolumab for a total of 5 months.

* *A female of childbearing potential is a sexually mature female who:*

- *Has not undergone a hysterectomy (the surgical removal of the uterus) or bilateral oophorectomy (the surgical removal of both ovaries) or*

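### Section 5.4.4 puts the lenalidomide and nivolumab contraception periods under a choose-one rule, whereas sections 3.1.6 and 3.1.9 make them cumulative for the patients they apply to

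*Combined protocol and SAP*

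**What the plan says.** Section 5.4.4 (Pregnancy) begins with a general instruction that patients "should use effective methods of contraception through defined periods during and after study treatment as specified below". Two lists follow.

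- **Women:** "Female patients must meet 1 of the following". The items are postmenopausal status, surgical sterility, a lenalidomide item (for those who could conceive: "agree to practice 2 effective methods of contraception from the time of signing of the informed consent form through 120 days", counted from the final lenalidomide dose), a nivolumab item ("agree to practice contraception for a period of 5 months after their last dose of nivolumab"), true abstinence, and a sentence ruling out periodic abstinence and withdrawal.
- **Men:** "must agree to 1 of the following". The items are a lenalidomide item ("Practice effective barrier contraception during the entire study treatment period and through 154 days after the last dose of lenalidomide"), a nivolumab item under which men sexually active with women of childbearing potential "must adhere to contraception for a period of 7 months after the last dose of nivolumab", true abstinence, and the same sentence on unacceptable methods.

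The eligibility criteria are built differently. Section 3.1.6 requires women of childbearing potential either to abstain or to begin two methods at least 28 days before lenalidomide. It requires contraception "for the duration of treatment with any study drug(s) plus 5 half-lives of study plus 30 days", given as 120 days after the last lenalidomide dose. A separate mandatory paragraph then sets 5 months after the last nivolumab dose. Section 3.1.9 requires men to use a latex condom through 154 days after lenalidomide, or to practise true abstinence. A separate mandatory paragraph sets 7 months after nivolumab for men sexually active with women of childbearing potential.

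**The concern.** Taken literally, the choose-one wording lets a patient satisfy 5.4.4 with one drug's item while falling short of 3.1.6 or 3.1.9. The two drug items stand at the same level as true alternatives such as sterility or abstinence, and nothing in the list joins them.

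This is a reproductive-safety instruction in the section that staff would consult during and after treatment. A patient following only the lenalidomide item could stop before the nivolumab period ends. A patient following only the nivolumab item would be working to a clock that takes no account of when lenalidomide stops. The endpoint, the sample size and the analysis are not involved.

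**Working it through.** The plan gives no figure to reproduce. The check is a comparison of the texts, followed by the day counts that the literal reading implies.

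**Side by side**

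| | 5.4.4 | 3.1.6 / 3.1.9 |
|---|---|---|
| Women, lenalidomide | 2 methods from consent through 120 days; one item of a choose-one list | Two methods from at least 28 days before, through 120 days; mandatory unless abstinent |
| Women, nivolumab | 5 months; another item of the same list | 5 months; separate mandatory paragraph |
| Men, lenalidomide | Effective barrier through 154 days; one item of a choose-one list | Latex condom through 154 days, or true abstinence |
| Men, nivolumab | 7 months; another item, with its own mandate for sexually active men | 7 months; separate mandatory paragraph for the same men |

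**Inputs**

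- Days required after lenalidomide: A = 120 (women), 154 (men).
- Months required after nivolumab, converted to days: 5 months = 152 (5 × 365/12 = 152.1; calendar range 150 to 153); 7 months = 213 (7 × 365/12 = 212.9; calendar range 212 to 215). Call this B. The conversion is an assumption.
- Schedule from section 5.1: 12 cycles of 28 days, nivolumab on days 1 and 15, lenalidomide on days 1 to 21.

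**Lenalidomide item used alone**

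With last doses on day N (nivolumab) and day L (lenalidomide), the shortfall is (N + B) − (L + A) = (B − A) − (L − N), and zero if that is negative.

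1. Both drugs stopped on the same day (L − N = 0). Women: 152 − 120 = 32 days (150 − 120 = 30 to 153 − 120 = 33). Men: 213 − 154 = 59 days (212 − 154 = 58 to 215 − 154 = 61).
2. Full undelayed course. Cycle 12 day 1 is 11 × 28 + 1 = day 309, so N = 323, L = 329 and L − N = 6. Women: 32 − 6 = 26 days (24 to 27). Men: 59 − 6 = 53 days (52 to 55).
3. The shortfall is zero once lenalidomide has run at least 33 days (women) or 61 days (men) past the last nivolumab dose, whatever the month lengths.
4. The hold. The protocol gives only the month, September 2017. If every last nivolumab dose fell on or before 30 September 2017, a patient still on lenalidomide at the version date of 23 January 2018 has L − N of at least 31 + 30 + 31 + 23 = 115 days. That exceeds 61, so the shortfall is zero. A last dose in August only lengthens the interval.

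**Nivolumab item used alone**

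This item states no two-method rule for women and no barrier rule to 154 days for men. Its clock also ignores continued lenalidomide. Take a last nivolumab dose on 30 September 2017 and lenalidomide still being taken on 23 January 2018. The nivolumab item then expires on 28 February 2018 (women) or 30 April 2018 (men). The lenalidomide requirement runs to at least 23 May (23 January + 120 days) or 26 June (+ 154 days). The differences are at least 84 and 57 days.

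**The case against.** The strongest reply is that the list was never meant as a strict menu. The sentence on periodic abstinence is printed as an item in both lists, yet nobody can choose it, so the choose-one rule cannot govern every bullet. The men's nivolumab item carries its own mandate and arguably binds those men whichever other item they pick. The lead-in also asks for contraception both during and after treatment. The intent was probably cumulative. The point about men stands and softens the conflict there. For women the nivolumab item has no such mandate, and probable intent does not replace operative wording.

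A second reply is that indentation may have been lost in the PDF text, as the criteria list in 3.1.2 suggests. That is a fair caution, but 5.4.4 does keep two list levels and each drug item is a complete clause.

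A third reply is that the rule is secured elsewhere. Sections 3.1.6 and 3.1.9 still apply, section 6.1 requires eligibility to be met on Cycle 1 Day 1, and REMS is mandatory (3.1.7, 3.1.8, 8.2.8). This stands, and it defeats a stronger conclusion that a reader might draw: that the protocol as a whole allows patients to stop contraception early. The documents do not support that. They contain one section that contradicts two others. REMS, however, is a lenalidomide programme, and nothing in the documents shows that it covers the months after nivolumab.

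**Conclusion.** The contradiction holds, and it is minor. Section 5.4.4 is wrong as written for women of childbearing potential. For men sexually active with such women it is at best ambiguous.

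On the lenalidomide item alone, the implied gap is 30 to 33 days (women) or 58 to 61 days (men) after a same-day stop, and about 26 or 53 days after a full course without delays. Treatment delays would shift these figures. The gap closes for anyone who stayed on lenalidomide long enough after nivolumab, which the hold made more likely. The opposite reading, relying on the nivolumab item while lenalidomide continues, is the one the hold leaves open; there 3.1.6, 3.1.9 and REMS provide the back-up.

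A reader might also infer that patients were exposed or misinformed. The documents give no last-dose dates and no count of patients concerned, and what patients were told at consent cannot be judged from them. The number affected may be zero.

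**What to change.** In each list of 5.4.4, replace the two drug items with one item joined by AND, in the terms of the eligibility criteria.

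- **Women of childbearing potential:** two methods begun at least 28 days before lenalidomide and kept through 120 days after its last dose, AND contraception through 5 months after the last nivolumab dose.
- **Men:** latex condom during treatment and through 154 days after the last lenalidomide dose, AND, if sexually active with women of childbearing potential, contraception through 7 months after the last nivolumab dose.

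Keep true abstinence as an alternative and, for women, postmenopausal or sterile status. Move the periodic-abstinence sentence out of the lists as a note. A simpler option is to replace both lists with a statement that all requirements of 3.1.6 and 3.1.9 apply. Joining the present 5.4.4 items without changing their terms would not be enough, because 5.4.4 starts the two methods at consent and asks men only for an effective barrier. Separately, 5.4.4 counts a woman as postmenopausal after 1 year, while the definition under 3.1.6 uses 24 months; that should be settled in the same amendment.

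Notify sites that have patients still within either window. If last nivolumab doses fell by 30 September 2017, the nivolumab windows close by 28 February 2018 (women) and 30 April 2018 (men), 36 and 97 days after the version date. The lenalidomide windows stay open for as long as patients remain on that drug, plus 120 or 154 days.

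The cost is a wording amendment to one section and a short site notice.
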